1.1.2. Treatment Assignment, Database Lock and Unblinding

1.1.2.1. Randomization

One hundred twenty (120) healthy subjects were to be randomized to vaccination or matching placebo (2:1). Eligible subjects were randomized to receive one administration of Sing2016 M2SR H3N2 influenza vaccine or saline placebo on Study Day 1. The randomization was a permuted block of size 3. Randomization was local to each site. The randomization was stratified on pre-screening antibody to HAI (<40 versus ≥ 40 to ≤ 320) obtained under a separate, site-specific ICF.

1.1.2.2. Database Lock

The clinical database will be locked after the last subject has completed visit 05/Day 29 QIV or has terminated the trial early and decisions regarding exclusion of individual subject data is documented following the Data Review meeting.

1.1.2.3. Treatment Blinding

ClinDart Data Management (DM) is responsible for supporting ongoing blinded data review and tracking throughout the study. DM will have access to treatment codes only after the database is locked. North Rim Consulting Statistician and programming staff will have access to treatment codes throughout the trial and will be responsible for managing information so as not to unblind other team members.

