5.6. Blinding

The blind will be maintained during this trial, including use of the following measures:

- 1. All subjects, whether receiving Sing2016 M2SR vaccine or placebo, will undergo the same procedures, i.e., administration, AE assessment, blood collections, nasal swabs, etc.
- 2. The unblinded pharmacist or designee will prepare doses (active and placebo), fill delivery devices and apply an opaque label to the device barrel to obscure any coloration of the contents.
- 3. The unblinded site staff and unblinded study monitor will agree to maintain the blind by not providing details of the dose (active or placebo) to any blinded clinic staff including the Investigator and to study subjects. Furthermore, the unblinded individuals will be restricted from participating in other study procedures the interpretation of which could be impacted by their unblinded status, such as evaluation of AEs.
- 4. If any blinded investigational site staff learn of treatment assignments, a record of the event will be maintained, and the Investigator will be informed. The Investigator will consult with FluGen on how to preserve the blind.
- 5. Labs supplied with subject samples for analyses will be blinded to treatment assignment.

Except for the unblinded statistician or computer programmer who generates the randomization list, the unblinded pharmacist(s) or their designee(s) who prepare the study product for administration and the unblinded study monitor who may observe the study product preparation and performs IP accountability, all subjects, the Investigator, statistical programmers and all

clinical site staff will be blinded to IP treatment (vaccine or placebo). All clinic staff who may be involved in making assessments of safety (including local reactions) will be blinded to treatment. Should a blinded monitor observe study product preparation, precautions must be taken to maintain the blind.

Masking of the IP (vaccine or placebo) will be described in the Pharmacy Manual.

The randomization schedule will be inaccessible to the Investigator or to the blinded study team (monitors and/or FluGen team) during the study. After the final study visit is complete for all subjects, after database lock, and after reconciliation with pharmacy and site records, the randomization code will be provided to the Study Statistician to enable data analysis by the Sponsor.

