8. STATISTICAL METHODS

The Statistical Analysis Plan (SAP), including table shells will be finalized prior to database lock. The final analysis will be completed after the last subject has had Visit 05 (28 days following the QIV dose) and the data base has been locked.

Analyses will be done using SAS software version 9.4 or higher.

Early reviews may be conducted on an expedited basis and included in an interim report, to aid in decision-making for future studies.

- Early reviews prior to database lock will be done on "snapshots" of the data available at the time of analysis. These snapshots will be stored as a permanent record of the trial.
- These reviews will not affect the conduct of this trial.
- Results will be presented by group; reports will display no subject level data.
- Personnel conducting immune response assays and conducting procedures or assessments of subjects will not have access to any data that would unblind them to individual subject treatment codes.

The SAP will elaborate on the analyses described here and will define which analyses would be included in an expedited report.

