1.1. Statistical and Analytical Plans

1.1.1. Definitions and General Considerations for Data Analysis

- 1. This Statistical Analysis Plan (SAP) is based on Clinical Trial Protocol FluGen-H3N2-V002-V005 dated 10-May-2021 (v2.0).
- 2. All programming and calculations will be performed using SAS statistical software, version 9.4 or later.
- 3. Study Day 1 is the day of randomization and 1st IP administration; QIV administration is planned 28 Days after IP administration
- 4. Baseline (IP Baseline) is the last observation prior to IP administration, at the datapoint, not the record level. For example, for laboratory values, individual repeat tests values will be used for baseline when the entire panel may not have been repeated.
- 5. Summaries will be presented by treatment and age group and for all ages combined. Cohorts 2 and 3 will not be presented separately.
- 6. This study is not powered to detect differences in safety or immunogenicity between active and placebo groups. The sample size of 120 (80 active subjects and 40 placebo subjects) was chosen empirically based on studies of other vaccines in early-stage development.
- 7. There is no plan for test of hypotheses; p-values generated for immunogenicity are descriptive only and not adjusted for multiplicity.
- 8. For transparency and traceability, raw data, not results from calculations or corrections are to be transferred from external vendors. Differences between data transferred versus data as analyzed, will be documented in the CSR.
- 9. The clinical database will be locked prior to final analyses of immunogenicity assays. Details regarding these analyses may be included as amendments to this SAP.

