4. PROTOCOL DEVIATIONS

N(%) of protocol deviations will be displayed by treatment and deviation type (missed visit, prohibited medication, missed procedure, procedure out of window, etc.). Major protocol violations and deviations will be reported in the clinical study report (CSR).

Before database lock, clinical operations, data management, medical and statistical staff will meet and agree on major protocol violations and deviations. Major deviations will exclude subjects from study populations at the Data Review meeting. See FluGen Protocol Deviation Handling Plan, Version 1.0 27 July 2021.

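### The SAP gives the contract statistician and programmers the treatment codes throughout the trial, an undeclared departure from the protocol, and does not keep code holders out of exclusion decisions or later immunogenicity addenda

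*SAP*

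**What the plan says.** **Who holds the codes.** Protocol 3.6.4 limits unblinding to the pharmacist or designee, the unblinded monitor, and the statistician or programmer who prepares the randomization list. Protocol 5.6 repeats that exception and then names those who stay blinded: "all subjects, the Investigator, statistical programmers and all" clinical site staff. Only after the last visit, database lock and reconciliation does it say that "the randomization code will be provided to the Study Statistician to enable data analysis by the Sponsor".

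SAP 1.1.2.3 differs: the contract "Statistician and programming staff will have access to treatment codes throughout the trial". These staff "will be responsible for managing information so as not to unblind other team members". Data management is treated more strictly: "DM will have access to treatment codes only after the database is locked". SAP Section 1 gives the SAP precedence over the protocol where they disagree. SAP Section 12, which lists changes to conduct and analysis, does not mention blinding.

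**Who decides exclusions.** Under SAP Section 4, before lock, "clinical operations, data management, medical and statistical staff will meet and agree on major protocol violations and deviations". Those decisions remove subjects from the study populations. SAP Section 2 applies them to IPEVAL and QIVEVAL through a judgement: whether a deviation is believed to affect the evaluation of immunogenicity. SAP 9.2.1 also assigns the eDiary summaries to IPEVAL, and solicited reactions are a primary endpoint in Protocol 2.2.1.

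**When immunogenicity rules are fixed.** SAP 1.1.1 item 9 places clinical lock before the final immunogenicity analyses and adds: "Details regarding these analyses may be included as amendments to this SAP". SAP 8.2 likewise allows assay details to be added as those analyses are finalized.

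**The concern.** A trial presented as double-blind relies on its analysis sets and analysis rules being settled by people who do not know the allocation. The SAP widens code access beyond what the protocol permits. It does not then separate the people with access from the two decisions where access matters: which subjects are dropped, and how an assay is analysed.

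At stake is whether the immunogenicity and reactogenicity results can be described as based on blinded decisions. No immunogenicity set free of deviation exclusions is planned as a check. Protocol 8.1 defines a full analysis set without them, but the populations in SAP Section 2 do not include it. The protocol already restricts unblinded people from procedures whose interpretation their knowledge could affect (3.6.4 and 5.6). The SAP does not extend that principle to the exclusion meeting.

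**Working it through.** The plan states no figure on this point, so the main check is a comparison of the texts.

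| Question | Protocol | SAP |
|---|---|---|
| Unblinded statistical roles before lock | Preparer of the randomization list only (3.6.4, 5.6) | Contract statistician and programming staff (1.1.2.3) |
| Statistical programmers | Blinded (5.6) | Hold codes throughout (1.1.2.3) |
| Study Statistician receives code | After last visit, lock and reconciliation (5.6) | Not delayed (1.1.2.3) |
| Departure declared | – | Not in Section 12 |

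1. *Is it a contradiction?* For programming staff, yes, directly. For the statistician, yes to the extent that the code holder is also the analyst, because the protocol's exception covers preparing the list. SAP Section 12 sends T-cell levels for analysis to an organisation whose initials match the contract group in 1.1.2.3, so that group appears to do the analyses.

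2. *Can code holders take part in exclusions?* Section 4 says statistical staff attend. The only statistical staff the SAP identifies are those holding codes. It names no blinded statistician and does not bar code holders. Their attendance is an inference; the absence of a bar is in the text.

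3. *Can rules be set after lock?* Item 9 puts lock before the final immunogenicity analyses, and 8.2 allows details to be added as those are finalized. Together they permit additions after lock, although neither uses those words. No deadline or blinding condition is attached.

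4. *Which outputs are exposed?* Those on IPEVAL and QIVEVAL: immunogenicity and the eDiary summaries. AE and SAE summaries use IPSS, which has no deviation-based exclusions.

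**Worst-case illustration.** The planned arms are 80 and 40 (SAP 1.1.1); the responder counts are assumed.

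- All subjects: 40/80 − 4/40 = 50.0% − 10.0% = 40.0 points.
- Drop 4 vaccine non-responders and 2 placebo responders: 40/76 − 2/38 = 52.6% − 5.3% = 47.4 points.
- Two-sided Fisher p is about 0.000015 before and 0.0000003 after, so the reading of this example does not change.
- A closer case: 20/80 vs 4/40 gives p = 0.057. Six exclusions chosen in one direction (20/78 vs 0/36) give 0.0003; chosen in the other (15/75 vs 4/39), 0.29.
- Six of 120 is 5.0%. If 120 is the base, six exclusions do not exceed the 5% trigger in SAP Section 2 for an additional per-protocol set.

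All of these require exclusions picked by arm and by response. They bound what could happen and predict nothing.

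**The case against.** **The protocol itself needs someone unblinded before lock.** It provides for an unblinded preparer of the list, allows the safety committee unblinded data on request, and permits early reviews by group. This stands, and it narrows the contradiction to the programming staff and to the code holder also being the analyst. A reader might also count the early reviews as a defect. The documents do not support that: Protocol 8 permits them on the terms "Results will be presented by group; reports will display no subject level data", and SAP 8.5 planned no interim review beyond the safety committee's.

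**Attendance is not stated.** A reader might infer that code holders decided exclusions. Section 4 says only that statistical staff attend, and it refers to a deviation handling plan, not supplied, that may set the criteria and attendance. Other safeguards exist: laboratories are blinded, data management is blinded until lock, exclusion decisions are documented before lock, and reasons for exclusion are listed. These reduce the risk, but none keeps code holders out of the decision.

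**Methods are largely fixed.** A reader might infer that immunogenicity methods can be chosen freely after lock. SAP 8.2 already sets the measures (GMT, GMFR, 2- and 4-fold rises, HAI of at least 40), the timepoints, t-tests and Fisher tests, and the IgA correction with its cut-off. What remains open is mainly added assay detail and the optional baseline adjustment, which has no stated criterion for imbalance.

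**The illustration is extreme.** Selecting by response requires subject-level assay results at the meeting, and nothing says they are available there. This stands, so the example serves only as a bound.

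**Version.** The SAP cites protocol v2.0; the protocol supplied is v3.0. The visible amendment items show no change to blinding.

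**Conclusion.** The point holds as an undeclared departure from the protocol's blinding, together with two missing safeguards. It should be corrected because the correction is cheap and the exposed results include a primary endpoint, solicited reactions, as well as the secondary immunogenicity endpoints.

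It does not show bias, and it does not reach the AE and SAE summaries. The study is descriptive: it tests no formal hypotheses and treats its p-values as descriptive only, which limits the consequence. The 40-to-47-point shift is a worst case on assumed counts.

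The conclusion rests on three readings: that the blinding text of protocol v2.0 matched v3.0, that item 9 and 8.2 together permit additions after lock, and that the unseen deviation handling plan does not already exclude code holders. If that plan does, the exclusion part reduces to a missing cross-reference.

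**What to change.** 1. **SAP Section 4.** State that anyone holding treatment codes takes no part in deciding exclusions and may supply blinded listings only. The blinded clinical operations, data management and medical members sign the exclusion list before lock, without by-group results or subject-level assay results.
2. **SAP 1.1.1 item 9 and 8.2.** Require each immunogenicity addendum to be signed before treatment codes are merged with that assay's data. Label any later change post hoc.
3. **SAP Section 12.** Declare the departure from Protocol 5.6. The SAP is dated 3 June 2022 and the protocol expected the last subject to finish in December 2021, so access during the trial can be disclosed but not reversed.

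**Cost.** SAP wording and meeting attendance. Assay details must be fixed earlier, and the exclusion decision is made without the code-holding statistician's vote. If the sponsor wants a statistician to vote, a blinded one would be needed, which could mean extra staff.

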2. ANALYSIS POPULATIONS

Five populations will be formed: Randomized Set, two Safety Sets, and two Evaluable Sets. If necessary two additional per protocol populations will be formed.

2.1.1.1. Randomized Set (RS) Population

The RS consists of all subjects randomized to the study. Results for this set will be reported by randomized treatment.

2.1.1.2. IP Safety Set (IPSS) Population

This SS Population will consist of all randomized subjects who receive any IP administration. Safety results will be presented by actual treatment received.

2.1.1.3. Safety Set (QIVSS) Population

This SS Population will consist of all randomized subjects who receive any QIV administration. Safety results will be presented by actual treatment received.

2.1.1.4. IP Evaluable Set (IPEVAL) Population

The IP Evaluable Set will consist of all randomized subjects who receive an IP administration, have an IP Day 29 visit with sample collection, and have no major protocol violations/deviations thought to interfere with evaluation of IP immunogenicity. Results for this set will be reported by randomized treatment. If more than 5% of this population is excluded due to major protocol deviations, then a new set (IPPPEVAL) will be formed, and analyses repeated using this population.

2.1.1.5. QIV Evaluable Set (QIVEVAL) Population

The QIV Evaluable Set will consist of all randomized subjects who receive an IP dose administration, receive QIV, have a QIV Day 29 visit with sample collection, and no major protocol violations or deviations thought to interfere with evaluation of immunogenicity. Results for this set will be reported by randomized treatment. If more than 5% of this population is excluded due to major protocol deviations, then a new set (QIVPPEVAL) will be formed, and analyses repeated using this population.

3. SUBJECT DISPOSITION (RS)

N(%) of Subjects will be accounted for as follows:

- 1. Randomized
- 2. Received IP administration (IPSS)
- 3. Received IP administration and had IP Day 29 visit with sampling
- 4. Received QIV administration (QIVSS)
- 5. Received IP dose and QIV administration and QIV Day 29 visit with sampling.

Reasons for exclusions from safety and evaluable sets will be

listed. Screen failures were not collected in the database.

4. PROTOCOL DEVIATIONS

N(%) of protocol deviations will be displayed by treatment and deviation type (missed visit, prohibited medication, missed procedure, procedure out of window, etc.). Major protocol violations and deviations will be reported in the clinical study report (CSR).

Before database lock, clinical operations, data management, medical and statistical staff will meet and agree on major protocol violations and deviations. Major deviations will exclude subjects from study populations at the Data Review meeting. See FluGen Protocol Deviation Handling Plan, Version 1.0 27 July 2021.

5. DEMOGRAPHIC AND BASELINE CHARACTERISTICS (IPSS)

N (%) of subject will be displayed by treatment for gender, race, age, ethnicity, height, weight, BMI, Investigational Site, baseline HAI from FluGen (<10, 10 - <40, >=40), and stratification HAI (<40, 40 - <=320). Summary statistics (N, Mean, SD, Median, Min,Max) will be displayed for continuous variables. N(%) will be displayed for categorical variables.

A second baseline will be necessary (QIV Baseline) to compute change from QIV baseline for vital signs, and immunogenicity.

6. MEDICAL HISTORY

Significant medical histories will be listed with condition and start and end dates. Medical histories with no end date will be reported as ongoing. There will be no summary of medical histories.

7. CONCOMITANT MEDICATIONS/THERAPIES (IPSS)

Medications will be collected beginning at informed consent, coded according to WHODrug Sep2019 and presented by therapeutic indication (ATC2) and preferred name. Concomitant medications will include all those taken during the study (Day 1—Day 29 QIV). Medications starting after informed consent and stopped prior to IP dosing will be included in the listings, but not included in the concomitant medications summary. Prohibited concomitant medications/therapies will not be flagged in these tables or listings. Prohibited medications/therapies will be appear under protocol deviations.

8. EFFICACY (ANALYSIS

8.1. Primary

Efficacy for this study is immunogenicity which is a secondary objective. The primary objective of this study is safety and tolerability.

8.2. Secondary

Immunogenicity will be assessed by measuring serum antibody responses by MN and/or HAI assay and mucosal antibody titers by ELISA. Additional immune parameters may be assessed including T cell responses. Samples are collected pre dose, at Day 29, and Days 1 and 29 QIV. Sample collection dates/times will be recorded in the clinical database.

Immunogenicity analyses will be analyzed as randomized. Additional details for specific immunogenicity assays may be added to this SAP as immunogenicity analyses are finalized.

Serum antibody response (influenza-specific HAI, MN, NAI, and ELISA results) will be summarized by treatment comparisons of GMT, GMFR, seroconversion, and seroprotection.

GMTs and GMFRs are displayed below by visit. Note that for approximately 40% of subjects, beginning at the end of September 2021, IP Day 29 and QIV Day 1 sample collection was on the same day.

Geometric Mean Titers and Mean Folds by Visit

Sample Collection	GMT	GMFR – reference
IP Day 1	X	
IP Day 29	X	IP Day 1
QIV Day 1	X	IP Day 1
QIV Day 29	X	QIV Day 1 & IP Day 1

Ln-transformed GMT and the ln-transformed GMFR ratios will be analyzed using t-tests. In case of baseline imbalance between treatments, analyses may be repeated using a general linear model adjusting for baseline titers.

Conversion rates categorized as >=2-fold and >= 4-fold will be reported for IP Day 29 and QIV Day 29. Treatment comparisons of conversion counts (%) will be done using Fishers Exact Tests. In case of baseline imbalance between treatments, analyses may be repeated using a logistic regression adjusting for baseline titers.

Seroprotection defined as HAI titer >=40 will be reported for IP Day 29 and QIV Day 29. Treatment comparisons of seroprotection counts (%) will be done using Fishers Exact Tests. In case of baseline imbalance between treatments, analyses may be repeated using a logistic regression adjusting for baseline titers.

Summary statistics for IgA response to influenza HA antigens are presented uncorrected and corrected for total IgA.

For the uncorrected analysis all samples are included regardless of total IgA(ug/mL).

For IgA corrected analysis

- \circ If Total IgA >= 1 then corrected value = Uncorrected/Total IgA.
- o If Total IgA < 1 then set the corrected value to missing.

For example: SingC = Sing / Total IgA >= 1; Else SingC = missing.

Summaries are GMTs, GMFRs, and N(%) of subjects with >= 2-fold and > = 4-fold rise in mucosal IgA. Summary statistics for secretory IgA immune response (influenza A-specific and total IgA ELISA) at IP Day 1, IP Day 29, and QIV Day 29 will be provided.

Depending upon the results of primary and secondary analyses, some or all the following exploratory analyses may not be done. Cell-mediated immunity (CMI) assessed by frequencies and fold-increases of antigen-specific T-lymphocytes may be summarized. Additional influenza-specific assays may be performed, and results summarized. Results of exploratory analyses may be reported separately from the CSR.

T Cell Mediated Immunity (Cytokines: IFNg, GrzB, IFNg+GrzB)

T Cell-mediated immunity (CMI) results are available for cells that secrete IFNg only, GrzB only, and cells that secrete both IFNg and GrzB. These double-secreting cells (IFNg+GrzB) will be a subset of cells that secret IFNg or GrzB only. CMI results are reported in Spot Forming Colonies (SFC) per 400,000 cells.

Summaries are GMTs, GMFRs, and N(%) of subjects with \geq = 2-fold and \geq = 4-fold rise in CMI. Summary statistics for CMI at IP Day 1 and IP Day 29 will be provided.

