8.4. Immunogenicity

Serum antibody, mucosal antibody response will be summarized using descriptive statistics by sampling timepoint for all subjects and by baseline values.

Seroconversion rates will be presented by timepoint and by baseline starting values.

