8.7. Examination of Subgroups

Due to the limited size of this study, there are no planned subgroup analyses. Exploratory analyses may examine primary or secondary endpoint results by age groupings, baseline titers or by QIV response, or those receiving Covid vaccine during the study.

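### Immunogenicity comparisons leave baseline titer out of the main analysis: unadjusted t-tests and pooled Fisher tests cost precision and dilute the seroprotection difference

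*SAP*

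**What the plan says.** **Continuous measures.** SAP 8.2: "Ln-transformed GMT and the ln-transformed GMFR ratios will be analyzed using t-tests". Adjustment is conditional and optional: "In case of baseline imbalance between treatments, analyses may be repeated using a general linear model adjusting for baseline titers". The same condition, with logistic regression, applies to the binary measures. No criterion for imbalance is given, and SAP 8.3 plans no other covariate.

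**Binary measures.** "Treatment comparisons of conversion counts (%) will be done using Fishers Exact Tests" and "Treatment comparisons of seroprotection counts (%) will be done using Fishers Exact Tests". Neither comparison is stratified. "Seroprotection defined as HAI titer >=40 will be reported for IP Day 29 and QIV Day 29".

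**Baseline in the design.** SAP 1.1.2.1: "The randomization was stratified on pre-screening antibody to HAI (<40 versus ≥ 40 to ≤ 320". Protocol 3.1 aims for about half of each cohort below 40. SAP 5 tabulates both the stratification HAI and a sponsor-laboratory baseline HAI. SAP 12 records that the sponsor-laboratory result replaced the screening result in data presentations.

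**Display by baseline.** Protocol 8.4: "Seroconversion rates will be presented by timepoint and by baseline starting values". SAP 8.7 says "there are no planned subgroup analyses" and leaves baseline titer as a grouping that exploratory work may use. SAP 1 gives the SAP precedence over the protocol.

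**The concern.** Baseline titer is likely to be the strongest available predictor of the Day 29 titer, and the trial already paid to balance it through stratification. The planned comparison of titers uses neither fact. The imbalance condition does not repair this. Stratified blocks are meant to prevent imbalance in HAI, so the condition should seldom be met, while the precision gained by adjusting does not depend on imbalance.

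For seroprotection, the endpoint threshold is also the stratum threshold. About half the subjects may meet the endpoint before dosing, and they can contribute little to a difference between arms.

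Immunogenicity is a secondary objective, intended to inform further development in older adults. What is at stake is the width of the reported intervals and the readability of the seroprotection contrast, not a formal error rate.

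**Working it through.** **Inputs from the documents.** 80 active and 40 placebo (SAP 1.1.1); about 50% with HAI <40 (Protocol 3.1); stratum and seroprotection thresholds both 40 (SAP 1.1.2.1 and 8.2).

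**Assumptions, because the documents give no values.** Baseline-post correlation r of 0.5 to 0.8, equal SDs at baseline and Day 29, the response rates below, and two-sided 0.05 for illustration only.

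**The plan's own figure.** The only computable one is the chance of seeing an AE of 20% prevalence in 15 subjects (Protocol 1.4): 1 − 0.8^15 = 0.965, which agrees with the stated >95%. It concerns safety. Nothing comparable exists for immunogenicity.

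**Step 1: reported variance.** In units of the Day 29 variance, the treatment contrast has variance 1 for the titer t-test, 2(1 − r) for the GMFR t-test and 1 − r² for the linear model with baseline (ANCOVA). The ratios are therefore 1 − r² and (1 + r)/2.

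**Step 2: true variance under stratification.** If the stratum is a median split of normal log titers in the same assay, stratifying removes a share 2/π ≈ 0.64 of the baseline variance. The true titer t-test variance is then about 1 − 0.64r², although the test still reports 1.

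| r | ANCOVA / titer t-test, reported | ANCOVA / GMFR t-test, reported | ANCOVA / titer t-test, true | Titer t-test type I error, simulated |
|---|---|---|---|---|
| 0.5 | 0.75 | 0.75 | 0.75/0.84 = 0.89 | 0.032 |
| 0.7 | 0.51 | 0.85 | 0.51/0.69 = 0.74 | 0.016 |
| 0.8 | 0.36 | 0.90 | 0.36/0.59 = 0.61 | 0.010 |

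Simulated ANCOVA type I error is 0.048–0.049, so the titer t-test is conservative, not inflated. The GMFR t-test is mildly conservative too (0.032, 0.040, 0.044). For an assumed effect of 0.5 SD, simulated power at r = 0.5 / 0.7 / 0.8 is 0.74 / 0.76 / 0.78 for the titer t-test, 0.74 / 0.92 / 0.985 for GMFR and 0.84 / 0.95 / 0.99 for ANCOVA.

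**Step 3: seroprotection.** If the ≥40 half stays ≥40, the pooled rate is 0.5 × 1 + 0.5 × p, where p is the rate in subjects starting <40. At 40% versus 10%, this gives 70% versus 55%: 30 points become 15. At 60% versus 10%, it gives 80% versus 55%: 50 points become 25. Simulated power, with strata split 50:50:

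| Rates in <40 stratum | Pooled Fisher | CMH (continuity-corrected) |
|---|---|---|
| 40% vs 10% | 0.20 | 0.71 (0.58) |
| 50% vs 10% | 0.57 | 0.91 (0.85) |
| 60% vs 10% | 0.88 | 0.99 (0.97) |
| 71% vs 5% | 1.00 | 1.00 (1.00) |
| 40% vs 10%, 20% of subjects in the wrong stratum | 0.30 | 0.44 (0.35) |

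If 97% rather than all of the ≥40 stratum stay protected, the first row becomes 0.22 versus 0.64 (0.51). A stratified test improves precision, but the weighted difference is still 0.5 × 30 + 0.5 × 0 = 15 points. Only a table by baseline shows the 30.

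**Step 4: the texts side by side.** Protocol 8.4 commits to seroconversion by baseline value. SAP 8.7 makes baseline groupings optional. SAP 12, which lists changes to planned analyses, does not mention it. This step needs no assumed number.

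**The case against.** The strongest reply is that little rests on these tests. Safety is primary, no hypothesis is formally tested, the study is not powered for a comparison of the arms, and every immunogenicity p-value is descriptive. The SAP also allows assay-specific detail to be added later. All of this stands. It lowers the stakes but is no reason to report wider intervals than the data require.

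A reader might also infer four stronger points that the documents do not support:

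- **That the plan switches models after seeing the data, making its p-values uninterpretable.** The t-tests and Fisher tests are done in any case. The adjusted model would be an addition, and its trigger is baseline, not outcome. The fault is that the trigger is undefined and optional.
- **That all four measures ignore baseline.** GMFR and seroconversion are built from each subject's own baseline. The GMFR excess is modest, and no loss was computed for seroconversion.
- **That the whole of 1 − r² is lost information.** Part of it is conservatism from ignoring the stratification.
- **That pooling masks a seroprotection effect.** It dilutes it. Pooled Fisher power is still 0.88 at 60% versus 10%, and the pooled difference remains a valid contrast for the population enrolled.

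Two limits also stand. The pre-screening HAI came from a separate site protocol, and the documents do not give the share at ≥40 in the sponsor's assay, so the halving is conditional. And Cohort 1, aged 50–64, has 10 versus 5 subjects, too few for a stratified comparison.

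**Conclusion.** The point holds as a matter of precision and clear presentation. For r of 0.5–0.8, adjustment gives 0.75–0.36 of the reported GMT variance and 0.75–0.90 of the reported GMFR variance. For GMT the true gain is smaller, at a ratio of about 0.89–0.61, given a median split in the same assay. On that basis the titer t-test on 120 subjects is worth an adjusted analysis of about 107 (120 × 0.89) down to 73 (120 × 0.61).

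Pooling shrinks the seroprotection difference to about half if about half of subjects start and stay ≥40 in the analysis assay. The power lost is large for moderate effects, smaller if the two HAI sources disagree, and nil for very large effects. The correlations, rates and significance level are all assumed.

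The unlisted departure from Protocol 8.4 rests on the text alone.

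**What to change.** Amend SAP 8.2, 8.3 and 12 as follows.

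- **Titers.** Make the main comparison a linear model of ln titer on treatment and ln baseline titer from the analysis laboratory, with age group added in the all-ages model. Report an adjusted GMT ratio with 95% CI. Use IP baseline for IP Day 29 and name the matching baseline for each QIV comparison. QIV Day 1 is measured after IP, so label results adjusted for it accordingly.
- **Seroconversion and seroprotection.** Compare the arms stratified by sponsor-laboratory baseline HAI <40 / ≥40, by an exact or CMH method, or by penalized logistic regression if cells are sparse. Do this for all ages or ages 65–85; give counts only for ages 50–64.
- **Tables.** Show both endpoints by baseline <40 / ≥40, which meets Protocol 8.4. If this is not done, list the departure in SAP 12.
- **Existing tests.** Keep the t-tests and Fisher tests as supportive, delete the imbalance condition, and keep all p-values descriptive.

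The cost is SAP wording, a few lines of model code and one or two tables. No new data are needed: baseline titers and both HAI classifications are already planned for collection or display.
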